2.2.6 Brush Allodynia

Dynamic mechanical brush allodynia will be tested by lightly brushing a 10 by 10 cm gauze pad bilaterally, 1-2 cm over each eyebrow at a rate of 2/second, for a total of 10 times. For each side of their forehead, subjects will be asked to assess the degree of pain elicited by the gauze on a scale of 0 to 10 with 0 being no pain and 10 being the worst imaginable pain.

2.2.7 Pharmacokinetics

The concentrations of Free ALD403 will be measured in plasma from all ALD403-treated subjects using validated assay methods. The PK analysis will include evaluations of concentration-time profiles for Free ALD403 at the following times: pre-dose on Day 0, and Weeks 4, 8, 12, 16, 20, 24, 36, 48, and 56.

Plasma collected at Week 4 from all placebo-treated subjects will be analyzed for the potential presence of Free ALD403 using validated assay methods.

2.2.8 Immunogenicity

Serum blood samples to test for antibodies to ALD403 will be taken pre-dose on Day 0, and Weeks 4, 8, 12,16, 20, 24, 36, 48, and 56. The immunogenicity will be assessed in serum from all ALD403-treated subjects using validated assay methods. Immunogenicity will not be assessed in placebo subjects.

For any samples that are positive for anti-ALD403 antibody, there may be additional testing to characterize the potential for neutralizing (NAb) ALD403 activity. Subjects who test positive for

specific anti-ALD403 antibodies at the time of the last study visit will be asked to provide up to 2 additional blood samples for immunogenicity testing at approximately 3 month intervals for up to 6 months. See the blinding plan for details concerning blinding and the capture of these samples.

2.3 Trial Day

Trial endpoints will be reported within analysis windows or analysis intervals based upon the actual date of the assessment. Assignment of results to these time points is based upon the trial day. Trial day is defined as:

Trial day = date of assessment - date of treatment

Analysis Windows used to report non-diary endpoints are outlined in Table 2.

Table 2: Analysis Windows

Visit	Range	Target Day	If more than one which one is used
			for analyses
Screening	< Day 0		First value
Day 0	Day 0 to Day 7	Day 0	Day 0
Week 4	Day 8 to Day 42	Day 28	Closest to Target Day
Week 8	Day 43 to Day 70	Day 56	Closest to Target Day
Week 12	Day 71 to Day 98	Day 84	Closest to Target Day
Week 16	Day 99 to Day 126	Day 112	Closest to Target Day
Week 20	Day 127 to Day 154	Day 140	Closest to Target Day
Week 24	Day 155 to Day 182	Day 168	Closest to Target Day
Week 28	Day 183 to Day 210	Day 196	Closest to Target Day
Week 36	Day 211 to Day 273	Day 252	Closest to Target Day
Week 48	Day 274 to Day 357	Day 336	Closest to Target Day
Week 56	> Day 357	Day 392	Closest to Target Day

Note: If two observations exist with same distance to target day, use first observation.

For the eDiary data used to produce the migraine and headache endpoints the intervals specified in Table 3 will be used to collapse the daily data into 4, 12, and 24 week intervals. For these data baseline is defined as the 28 days starting on the day of the first diary entry.

Table 3: eDiary Headache/Migraine Endpoint Analysis Intervals

Diary			
Weeks	Trial Time	Comments	Endpoints
Baseline	The 28 days starting from the first eDiary entry		All eDiary related endpoints
1-4	Days: 0-27	Day 0 = First day of treatment	All eDiary related endpoints
5-8	Days: 28-55		All eDiary related endpoints
9-12	Days: 56-83		All eDiary related endpoints
1-12	Weeks 1-4, 5-8 and 9-12	Average of the 4 week intervals after imputation methods are applied	All Primary and Secondary eDiary related endpoints
13-16	Days: 84-111		All eDiary related endpoints
17-20	Days: 112-139		All eDiary related endpoints
21-24	Days: 140-167		All eDiary related endpoints
13-24	Weeks 13-16, 17-20 and 21-24	Average of the 4 week intervals after imputation methods are applied	All Primary and Secondary eDiary related endpoints
1-24	Weeks 1-4, 5-8, 9-12, 13-16, 17-20 and 21-24	Average of the 4 week intervals after imputation methods are applied	All Primary and Secondary eDiary related endpoints
25-28	Days: 168-195	1 11	All eDiary related endpoints
29-32	Days: 196-223		All eDiary related endpoints
33-36	Days: 224-251		All eDiary related endpoints
25-36	Weeks 25-28, 29-32 and 33-36	Average of the 4 week intervals after imputation methods are applied	All Primary and Secondary eDiary related endpoints
37-40	Days:252-279	•	All eDiary related endpoints
41-44	Days: 280-307		All eDiary related endpoints
45-48	Days: 308-335		All eDiary related endpoints
37-48	Weeks 37-40, 41-44 and 45-48	Average of the 4 week intervals after imputation methods are applied	All Primary and Secondary eDiary related endpoints
25-48	Weeks 25-28, 29-32, 33-36, 37-40, 41-44 and 45-48	Average of the 4 week intervals after imputation methods are applied	All Primary and Secondary eDiary related endpoints

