- 10. Not to use any approved devices, neuromodulation, neurostimulation or injectable therapy (trigger point injections, extracranial nerve blocks, facet joint injections) for headache prophylaxis are prohibited 2 months prior to screening and during the 28 day period prior to randomization
- 11. Women of child-bearing potential, and males with partners of child-bearing potential, must agree to use adequate contraception throughout study participation and for up to six months after last dose. Adequate contraception includes oral, transdermal or injectable [depot] estrogen, and/or progestogen, selective estrogen receptor modulator contraceptive therapy, intrauterine contraceptive device, double barrier method (e.g., condom and diaphragm or spermicidal gel) or vasectomy. Non-childbearing potential is defined as post-menopausal for at least 1 year or surgical sterilization or hysterectomy at least 3 months before screening.
- 12. Any hormonal therapy (e.g., contraceptives, hormone replacement therapy) use is stable and ongoing for at least 3 months prior to screening and through Week 56
- 13. Willing, committed, and able to comply with scheduled clinic visits and complete all trial-related procedures
- 14. Headache eDiary was completed on at least 25 of the 28 days prior to randomization

- 15. Subject agrees not to post any personal medical data related to the trial or information related to the trial on any website or social media site (e.g., Facebook, Twitter) during the trial
- 16. Subject is willing to complete the daily eDiary for the duration of the study and agrees to use the eDiary device for the sole purpose of the ALD403-CLIN-006 study without alteration

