10.2 Day 0 (Randomization and Treatment)

Day 0 must be 29 to 35 days after the screening visit.

The following assessments will be performed pre-dose (unless otherwise specified) and measurements recorded with review of data from eDiary:

- Review inclusion/exclusion criteria including:
 - o Verification of completion of eDiary for at least 25 of 28 days following screening
 - Verification that during the 28 day period following screening, the subject experienced ≤ 14 headache days of which at least 4 have to be migraine days (migraine days count as headache days) as recorded in the eDiary.
- Body weight
- Physical examination
- Brush allodynia test
- Vital signs including BP and pulse
 - Vital signs will be obtained and recorded prior to the start of Investigational Product infusion and 4 hours post-end of infusion (± 30 minutes).
- C-SSRS Since Last Visit Version
- 12-lead ECG
 - 12-lead ECGs will be performed prior to the start of Investigational Product infusion and 4 hours post-end of infusion (± 30 minutes)
- Clinical laboratory tests, including hematology and serum chemistry
- Pregnancy test (urinary hCG) on all female subjects
 - Subjects with a positive pregnancy test will not be dosed and will be withdrawn from the trial
- Plasma Free ALD403 PK sample
 - Blood will be drawn pre-dose (within one hour prior to Investigational Product administration)
- A blood sample will be taken pre-dose for baseline determination of anti-ALD403 antibodies in serum (immunogenicity)
- SF-36 v2.0, EQ-5D-5L and ASC-12 completion by subject
- Adverse events (throughout visit)
- Concomitant medications (throughout visit)
- Randomize subject via the IWRS or IVRS system

 Dosing of ALD403 or Placebo; subject must be monitored for at least 4 hours after the dosing completion

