13.3 General Considerations

13.3.1 Definition of Baseline

Baseline for migraine and headache endpoints will be based upon the data recorded in the headache eDiary during the 28-days following screening. For other variables, the baseline assessment will be the latest available valid measurement taken prior to the administration of Investigational Product. This will generally be Day 0.

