2.2 Clinical Trial Endpoints

The efficacy, safety, pharmacokinetic and immunogenicity of ALD403 will be assessed using the following endpoints. Greater detail concerning these endpoints can be found in Section 2.2.2.

Primary Efficacy Endpoint

• Change in frequency of migraine days (Weeks 1-12)

Key Secondary Efficacy Endpoints

- 75% migraine responder rate (Weeks 1-4)
- 75% migraine responder rate (Weeks 1-12)
- 50% migraine responder rate (Weeks 1-12)
- Percentage of subjects with a migraine on the day after dosing

Other Secondary Efficacy Endpoints

- Change in acute migraine medication days (Weeks 1-12)
- Headaches/Migraines with acute medication usage
- 100% migraine responder rates (Weeks 1-12)
- Short-Form Health Survey (SF-36 v 2.0)
- Health-Related Quality of Life (EQ-5D-5L)
- Allodynia Symptom Checklist-12 (ASC-12)
- Brush (dynamic mechanical) Allodynia
- Migraine responder rates for time periods other than Weeks 1-12
- Change in frequency of migraine days between baseline and time periods other than Weeks 1-12
- Headache responder rates
- Change in the frequency of headache days
- Percent change in headache/migraine days
- Time to first migraine after dosing
- Headache/Migraine hours
- Headache/migraines with severe intensity

Tertiary Endpoints

• Headache episodes/migraine attacks

Exploratory Endpoints

- Headache/Migraine characteristics
- Headaches/Migraines with type of acute medication usage
- Headache episode/Migraine attack average length

Safety Endpoints

- Adverse events (AEs) and serious adverse events (SAEs)
- Changes in clinical laboratory assessments
- Vital Signs
- ECGs
- Suicidal ideation and behavior as measured by the Columbia-Suicide Severity Rating Scale (C-SSRS)

Pharmacokinetic Endpoints

• Free ALD403 plasma concentrations

Immunogenicity Endpoints

- Development of specific anti-ALD403 antibodies
- Characterization of specific anti-ALD403 antibodies for neutralizing activity

2.2.1 eDiary

Subjects will complete a daily headache eDiary from the time of screening to Week 48. The diary is to be completed each trial day whether or not the subject had a headache. These daily entries record if the subject took acute migraine medication on that day.

The eDiary data from the 28 days following screening visit will be used to determine eligibility criteria, and the baseline migraine and headache results.

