3.2 Definition of Baseline

Baseline assessment for migraine and headache endpoints will be based upon the data recorded in the headache eDiary during the 28 days following screening. For other variables, the baseline assessment will be the latest available valid measurement taken prior to the administration of Investigational Product. This will generally be Day 0.

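### SAP 2.3 and Table 3 start the 28-day diary baseline at the first entry with no stop at Day -1, so a few eligible subjects could have post-dose days in both baseline and Weeks 1-4

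*SAP*

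**What the plan says.** **Baseline from the first entry.** SAP 2.3: "For these data baseline is defined as the 28 days starting on the day of the first diary entry". The baseline row of Table 3 repeats it: "The 28 days starting from the first eDiary entry". Neither sets a last permissible day.

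**Baseline from screening.** SAP 3.2 bases it on "data recorded in the headache eDiary during the 28 days following screening". SAP 2.2.1 uses one window for both eligibility and baseline; its sentence opens "The eDiary data from the 28 days following screening visit will be used to determine eligibility". Protocol 13.3.1 refers to the "headache eDiary during the 28-days following screening". Protocol 12.1.1 and the synopsis agree.

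**Timing and compliance.** Protocol 10.2 puts Day 0 at 29 to 35 days after the screening visit and lists as a Day 0 check "Verification of completion of eDiary for at least 25 of 28 days following screening". Inclusion criterion 14 (Protocol 8.1) applies the same 25-of-28 threshold to the days before randomization: "Headache eDiary was completed on at least 25 of the 28 days prior to randomization". SAP Table 3 assigns Days 0-27 to Weeks 1-4, with Day 0 the first day of treatment.

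**The concern.** Table 3 is the specification that turns daily diary records into analysis intervals, so a programmer could reasonably follow it rather than SAP 3.2. For a subject whose first entry comes late, the two rules give different baselines. If Day 0 also comes early in its permitted range, the Table 3 baseline runs past dosing.

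Baseline migraine days are the reference for the primary change, the ANCOVA covariate and the denominator of the 50% and 75% responder endpoints in the serial testing procedure. A baseline containing post-dose days is no longer a pre-treatment measurement, and the same days would count on both sides of the change.

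**Working it through.** **1. The plan's own figure.** SAP 1.5: 200 per arm, effect 1 day, two-sided 5%, SD 2.7 (at least 95% power) or SD 3 (90%). Power = Φ(effect / (SD × √(2/200)) − 1.96).
- SD 2.7: Φ(3.704 − 1.96) = 95.9%.
- SD 3: Φ(3.333 − 1.96) = 91.5%.

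Both statements reproduce.

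**2. Day arithmetic under Table 3.** Let g be the days from screening to Day 0 (29 to 35) and k the days by which the first entry is late (0 to 3, since 25 of 28 are required and nothing stops the missed days being the first ones). The documents do not say whether the 28 days start on the screening day or the day after, so both counts are shown.
- Screening-day count: first entry on Day −g + k, baseline ends on Day −g + k + 27, shared days = max(0, 28 + k − g).
- Day-after count: everything moves one day later, shared days = max(0, 29 + k − g).

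| Gap g | Shared days for k = 0, 1, 2, 3 (screening-day count) | Shared days for k = 0, 1, 2, 3 (day-after count) |
|---|---|---|
| 29 | 0, 0, 1, 2 | 0, 1, 2, 3 |
| 30 | 0, 0, 0, 1 | 0, 0, 1, 2 |
| 31 | 0, 0, 0, 0 | 0, 0, 0, 1 |
| 32-35 | none | none |

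The largest case on the day-after count is screening on Day −29 with first entry on Day −25. Days −25 to −1 give 25 completed days, which satisfies both the Day 0 check and inclusion 14, and baseline ends on Day −25 + 27 = Day 2. On the screening-day count that subject has 24 of the 28 days −29 to −2 and fails the Day 0 check, so the maximum there is 2 days.

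**3. Effect on the contrast.** Assume the full effect applies from Day 0. With m shared days, the baseline difference between arms moves by m/28 of the effect. For a 1-day effect this is 2/28 = 0.07 day or 3/28 = 0.11 day per affected subject. The share of subjects affected is not in the documents, so the rows below are assumptions, without covariate adjustment:

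| Share with 3 shared days | Mean effect | Power, SD 2.7 | Power, SD 3 |
|---|---|---|---|
| 0% | 1.000 | 95.9% | 91.5% |
| 10% | 1 − 0.1 × 3/28 = 0.989 | 95.6% | about 91% |
| 100% (extreme) | 1 − 3/28 = 0.893 | 91.1% | 84.5% |

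**4. Effect on one subject.** Take a subject whose rate falls from 8 to 4 migraine days per 28, exactly a 50% responder. With 3 shared days, baseline = 8 × 25/28 + 4 × 3/28 = 7.57 and the reduction is (7.57 − 4)/7.57 = 47.2%, a non-responder.

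**5. The conflict without overlap.** Take a subject with the first 3 screening days unfilled and 7 migraine days on the other 25. The SAP 3.2 window with Missing Data Rule 1 gives 7 × 28/25 = 7.84. Table 3 instead adds the next 3 calendar days and gives 7 to 10 if those days are completed.

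**6. Under the screening-based rule.** The window ends on Day −g + 27, between Day −8 and Day −2, or one day later, between Day −7 and Day −1. There is no overlap at any permitted gap.

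**The case against.** **Most subjects are untouched.** The diary is handed out with instructions at the screening visit (Protocol 10.1) and is to be filled in daily from then on. A subject who starts on time has no overlap at any permitted gap. This stands, and it is why the effect is small.

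**SAP 1.2 may close the gap.** It determines eligibility from the initial 28 days of diary data after screening, and SAP 1.3 has randomization follow verified eligibility. If that means 28 days must elapse from the first entry, no post-dose day can enter. But Protocol 10.2 ties the check to screening, and no text requires the wait. The reading is possible but not established.

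**Stronger readings.** A reader might infer three competing baselines by adding inclusion 14. That criterion governs compliance and does not define a baseline. A reader might also combine a 3-day overlap with a 7-day gap between the two compliance windows when screening is on Day −35. Those figures need different counts. Counting from the screening day, the windows are Days −35 to −8 and −28 to −1, 7 days apart, but the overlap is at most 2 days. Counting from the day after, the overlap can reach 3 days, but the windows differ by at most 6. Finally, a reader might want inclusion 14, the Day 0 check and stratification realigned. A footnote to Protocol Table 5.3 says enrollment is complete, so those steps have already been applied.

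**Conclusion.** The point holds in a narrow form. The SAP carries two definitions of the diary baseline, and the one in SAP 2.3 and Table 3 permits post-dose days, which are then also counted in Weeks 1-4. The overlap needs a late first entry, few or no other missed days, and dosing 29-30 days after screening (29-31 on the day-after count).

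The contrast is attenuated by at most about 0.11 day per affected subject for a 1-day effect, assuming full effect from Day 0. A slower onset gives less, and adjusting for baseline in the ANCOVA should reduce it further. A reader might infer a bias in favor of ALD403. The documents do not support that: a late first entry precedes randomization, so its frequency does not depend on arm, and the effect on a true difference is toward zero. Individual responder classifications near a threshold can change, but nothing suggests that the trial's conclusions depend on this. It is a small error in the definition of a primary-endpoint input and worth correcting.

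**What to change.** Before the Week 24 unblinding described in SAP 1.4:
- Replace the baseline sentence in SAP 2.3 and the baseline row of Table 3 with the SAP 3.2 definition.
- State whether the screening day is the first of the 28 days.
- State that no day on or after Day 0 enters the baseline.
- State that unfilled baseline days are handled by Missing Data Rule 1.

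Capping the first-entry window at Day −1 would also remove the overlap, but it would leave the conflict with SAP 2.2.1, SAP 3.2 and the protocol.

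The cost is a short SAP edit and a check of the baseline derivation program; no new data are needed. A subject with 3 unfilled days has a baseline scaled up by 28/25 = 1.12 from 25 observed days, which adds slight noise for that subject. Eligibility and stratification are left as applied.

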2.4 Pooling Strategy for Strata

No pooling will be done.

2.5 Statistical Assessment of the Trial Objectives

Hypothesis testing will be performed for the primary endpoint: change from baseline in migraine days from Weeks 1-12. This endpoint will be calculated as outlined in Section 2.2.2 and will utilize the missing data rules provided in Section 2.7.2. The hypotheses tested are

$$H_o: \Delta_{plb} = \Delta_{403} H_a: \Delta_{plb} \neq \Delta_{403}$$

where Δ_{403} is the change in migraine days for subjects in the ALD403 treatment arm and Δ_{plb} is similarly defined for the placebo subjects. The change from baseline is expected to be negative as migraines are being reduced. While the test outlined above is two sided, as is the alpha level used for this study (i.e. 5%), clinically relevant results require a larger reduction of migraines on the ALD403 arms.

An ANCOVA model will be used to test for a difference between treatment arms. This model will include the change from baseline measure as the response variable. Treatment and the stratification variable: baseline migraine days (continuous covariate) will be the independent variables.

In addition, model based estimates including confidence intervals for the treatment differences will be used to summarize the results for the primary endpoint.

A sensitivity analysis of the change from baseline in migraine days will be performed using the sensitivity missing data rule provided in Section 2.7.2.

Secondary Efficacy Analyses

Summary statistics including confidence interval for the treatment differences will be used to summarize the results for the secondary endpoints. Testing will be performed for the key secondary endpoints and for the change in acute migraine medication days endpoint. For the key secondary endpoints (responder rates and percentage of subjects with a migraine on the day after dosing) this testing will utilize a CMH/extended CMH test. The tests will be stratified by the randomization stratification factor. The change in acute migraine medication day endpoints will be tested using an ANCOVA model similar to the one used for the primary endpoints: change from baseline measure as the response, treatment and baseline acute migraine medication days as independent variables. The time to first migraine analysis will be descriptively summarized based upon Kaplan-Meier methods.

Exploratory Analyses

Exploratory endpoints will be summarized with descriptive statistics by treatment group.

20

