13.4.2 Efficacy Analyses

Efficacy endpoints will be summarized with descriptive statistics. The migraine and headache endpoints will be summarized by four, twelve and twenty-four week intervals with the remaining endpoints being summarized by study week.

Primary Efficacy Analyses

Hypothesis testing will be performed for the primary endpoint: change from baseline in migraine days from Weeks 1-12. This endpoint will be calculated as outlined in Section 12.1.2 and will utilize the missing data rules provided in Section 13.3.2. The hypotheses tested are

$$H_o$$
: $\Delta_{plb} = \Delta_{403}$ H_a : $\Delta_{plb} \neq \Delta_{403}$

where Δ_{403} is the change in migraine days for subjects in the ALD403 treatment arm and Δ_{plb} is similarly defined for the placebo subjects. The change from baseline is expected to be negative as migraines are being reduced. While the test outlined above is two sided, as is the alpha level used for this study (i.e. 5%), clinically relevant results require a larger reduction of migraines on the ALD403 arms.

An ANCOVA model will be used to test for a difference between treatment arms. This model will include the change from baseline measure as the response variable. Treatment and the stratification variable: baseline migraine days (continuous predictor) will be the independent variables.

Secondary Efficacy Analyses

Summary statistics including confidence interval for the treatment differences will be used to summarize the results for the secondary endpoints. Testing will be performed for the key secondary endpoints and for the change in acute migraine medication days endpoint. For the key secondary endpoints (responder rates and percentage of subjects with a migraine on the day after dosing) this testing will utilize a CMH/extended CMH test. The tests will be stratified by the randomization stratification factor. The change in acute migraine medication day endpoints will be tested using an ANCOVA model similar to the one used for the primary endpoints: change from baseline measure as the response, treatment and baseline acute migraine medication days as

independent variables. The time to first migraine analysis will be descriptively summarized based upon Kaplan-Meier methods.

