1.3 Method of Assigning Subjects to Treatment Groups

Randomization will occur 29 to 35 days after the screening visit when the eligibility assessments are completed and eligibility verified. Sites will complete the randomization using an Interactive Web Response System (IWRS) and the randomization assignment will be obtained by the clinical trial site's unblinded pharmacist or Investigational Product consignee. Subjects will be randomized in equal ratios to one of the four 4 treatment groups (30 mg, 100 mg, or 300 mg of ALD403 or Placebo). Stratified permuted block randomization will be used. Stratification will be by migraine days during the screening period (≤9 days vs. >9 days).

Randomized subjects who terminate their clinical trial participation for any reason, regardless of whether Investigational Product was taken or not, will retain their randomization assignment and subject number.

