3.4 Analysis of Efficacy Endpoints

3.4.1 Headache/Migraine Days and Acute Migraine Medication Days

Summary tables for the number of migraine/headache days, change from baseline and the percent change by 4, 12 and 24 week intervals and treatment group will be produced. Similar tables will be produced for acute migraine medication days and the change from baseline acute migraine medication days. The treatment difference and associated confidence interval will also be provided. These confidence intervals will be based on normal approximation. Stratification will not be used for these intervals.

Additionally, the SAS procedure, Proc Mixed using the ANCOVA model controlling for the effects of baseline migraine days outlined in Section 2.5, will be used to calculate the estimated treatment difference from placebo, the change from baseline and the associated confidence intervals for Weeks 1-12. The ANCOVA model will also be used to test for a treatment difference in the primary endpoint change from baseline in migraine days for Weeks 1-12 and for the change from baseline days of acute migraine medication use for Weeks 1-12. Significant p-values based on the formal decision rule criteria outlined in Section 2.7.5 will be clearly noted.

Plots of the migraine days and change from baseline and for days of acute migraine medication use and change from baseline will be produced. These plots will use the four week intervals as

the X-axis. A separate set of graphs that provide histograms of the Week 1 to 12 results for these three parameters will also be produced.

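### The explicit ANCOVA for change in acute migraine medication days leaves out the migraine-day factor used to stratify randomisation, at a small cost in precision, and SAP 3.4.1 refers to that model loosely

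*SAP*

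**What the plan says.** - **Randomisation.** SAP 1.3: "Stratification will be by migraine days during the screening period", cut at ≤9 vs >9 days, with permuted blocks. Protocol 8.3.2 says the same.
- **Primary endpoint.** SAP 2.5: "Treatment and the stratification variable: baseline migraine days (continuous covariate) will be the independent variables".
- **Key secondary endpoints.** SAP 2.5 and Protocol 13.4.2 use CMH or extended CMH tests stratified by the randomisation factor.
- **Medication days.** SAP 2.5: "Testing will be performed for the key secondary endpoints and for the change in acute migraine medication days endpoint". The model for the latter is "change from baseline measure as the response, treatment and baseline acute migraine medication days as independent variables". Protocol 13.4.2 gives the same two terms: "treatment and baseline acute migraine medication days as" independent variables. Both call it similar to the primary model.
- **Implementation.** SAP 3.4.1 covers migraine days and medication days together. It names "Proc Mixed using the ANCOVA model controlling for the effects of baseline migraine days outlined in Section 2.5", and its next sentence begins "The ANCOVA model will also be used to test for a treatment difference in the primary endpoint" and goes on to include change in medication-use days for Weeks 1-12. It does not mention baseline medication days as a covariate.
- **Standing of the endpoint.** SAP 2.2 lists it under other secondary endpoints. SAP 2.7.5 does not name it in the serial procedure.

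**The concern.** Under its explicit model, this is the only tested efficacy endpoint with no term for the variable that randomisation was stratified on, and the documents give no reason. Stratified allocation balances the arms on migraine days. If migraine days predict change in medication use beyond what baseline medication use predicts, a model without them leaves that variation in the residual. The reported standard error then does not reflect the balance that the design has secured.

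The wording of SAP 3.4.1 adds a smaller practical risk. A programmer working from that section alone could fit baseline migraine days as the only covariate and leave out the endpoint's own baseline. The two models give different estimates, intervals and p-values for an endpoint that Amendment 4 added at the FDA's request.

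**Working it through.** **Which terms each tested analysis carries**

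| Analysis | Own baseline | Migraine-day factor |
|---|---|---|
| Primary ANCOVA (SAP 2.5) | yes (the same variable) | yes, continuous |
| Key secondary CMH (SAP 2.5) | built into the responder definition; none for the day-after-dosing endpoint | yes, stratum |
| Medication days, SAP 2.5 and Protocol 13.4.2 | yes | no |
| Medication days, SAP 3.4.1 read literally | no | yes, continuous |

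**The plan's own figures.** Protocol 13.2 and SAP 1.5 give no effect, SD or power for medication days. The primary power does reproduce. With 200 per arm and a 1-day effect, the noncentrality is 1/(SD × √(2/200)): 3.70 at SD 2.7 and 3.33 at SD 3. Two-sided 5% t-test power on 398 df is 95.9% and 91.4%, against the stated 95% and 90%. Nothing below changes the sample size.

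**Simulation 1: residual variance.** Assumptions: baseline migraine days restricted to 4-14; 40-100% of subjects using a triptan or ergot; mean-use parameter 0.3-0.9 of migraine days; binomial medication days given migraine days; a 12-week average afterwards. Residual variance relative to a model with both covariates:
- own baseline only (SAP 2.5): ratio 1.001-1.029, that is 0-3% more; √1.029 = 1.014, so the standard error is at most about 1.4% larger;
- migraine days only (literal SAP 3.4.1): ratio 1.125-2.454; √ gives 1.06-1.57.

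**Simulation 2: type I error and power.** Two arms of 200, balanced within the ≤9 and >9 strata, 4,000 runs per setting. Assumptions: baseline medication days with mean 2 and SD 2; correlation ρ of 0.3 or 0.6 with migraine days; slope −0.5 on baseline medication days; extra effect b of migraine days of 0, 0.5 or 1.0 day per SD; residual SD 2; treatment effect 0 or 0.6 day. Models: A = own baseline (SAP 2.5); B = migraine days only (literal SAP 3.4.1); C = A plus stratum; D = A plus continuous migraine days.

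| ρ | b | Reported SE A / B / D | Power % A / B / C / D |
|---|---|---|---|
| 0.3 | 0 | 0.200 / 0.222 / 0.200 | 84.5 / 77.2 / 84.4 / 84.5 |
| 0.3 | 0.5 | 0.206 / 0.221 / 0.200 | 82.8 / 77.3 / 83.7 / 84.4 |
| 0.3 | 1.0 | 0.222 / 0.221 / 0.200 | 78.7 / 78.1 / 82.3 / 85.3 |
| 0.6 | 0 | 0.200 / 0.215 / 0.200 | 83.6 / 77.7 / 83.6 / 83.7 |
| 0.6 | 0.5 | 0.204 / 0.216 / 0.200 | 83.7 / 79.4 / 84.2 / 84.7 |
| 0.6 | 1.0 | 0.216 / 0.215 / 0.200 | 80.5 / 79.1 / 82.2 / 84.8 |

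The standard errors agree with a hand calculation. SE ≈ √(2/200) × √(residual variance). For A the residual variance is about 4 + b²(1 − ρ²). At ρ = 0.3 and b = 1.0 that is 4.91, so SE = 0.1 × 2.216 = 0.222. For D it is 4, so SE = 0.200.

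- **Bias:** about 0 for all four models.
- **Type I error:** 4.2%-5.2% for A; 4.6%-5.7% across B, C and D (Monte Carlo SE about 0.35 points).
- **Why A is conservative:** at ρ = 0.3, b = 1.0 and no effect, the estimates under A had an SD of 0.213 but a mean reported SE of 0.222. Stratification had already improved the estimate, and the reported SE did not show it.
- **Gain from D over A:** 0 to 85.3 − 78.7, about 7 points. From C over A: 0 to about 4 points.
- **B against A:** lower power in every setting, by about 0.5 to 7 points.

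The simulations differ at the upper end because simulation 2 lets migraine days act directly on the change score. Its extreme setting implies 4.91/4 = 1.23 times the residual variance of D.

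**The case against.** The strongest case against is that the plan is already clear and valid. SAP 2.5 and Protocol 13.4.2 give this endpoint its own explicit model, and they agree. SAP 3.4.1 refers back to Section 2.5, so the specific statement should govern. ANCOVA on an endpoint's own baseline is a standard pre-specified analysis. All of this stands. It makes SAP 3.4.1 a loose cross-reference, and the absence of the migraine-day term under the governing model remains.

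A reader might infer more than the documents support:
- **That the stratum is ignored on either reading.** It is absent only under SAP 2.5. The literal SAP 3.4.1 model contains baseline migraine days, which the SAP itself calls the stratification variable; what that reading drops is the endpoint's own baseline. The two gaps are alternatives.
- **That the test is invalid or could produce false positives.** Neither bias nor type I error inflation appeared.
- **That a large loss of precision is likely.** The 12-145% increase in residual variance in simulation 1 belongs to the less likely reading and depends on assumed inputs. In simulation 2 the same reading widens the SE by only about 7-11% (0.215/0.200 to 0.222/0.200).
- **That the FDA's request raises the stakes for the model.** The Amendment 4 change table records a request to add the endpoint and does not attribute any particular model to that request.

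**Conclusion.** The point holds as a minor improvement. The explicit model for a tested other secondary endpoint leaves out the stratification variable that the primary and key secondary analyses carry. The consequence is a neutral to slightly conservative test: 0-3% more residual variance in one simulation, and 0 to about 7 power points lost in the other. These sizes rest wholly on assumed inputs; the direction does not, since a prognostic stratification variable left out of the model can only leave the reported SE the same or too wide, apart from chance and the single degree of freedom.

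The SAP 3.4.1 wording is a separate editorial defect. It would matter more only if it were followed in place of SAP 2.5. The endpoint is outside the serial procedure, so no multiplicity-controlled claim depends on it.

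**What to change.** - **SAP 2.5 and Protocol 13.4.2:** for change in acute migraine medication days (Weeks 1-12), list treatment, baseline acute migraine medication days (continuous) and baseline migraine days (continuous, as in the primary model).
- **SAP 3.4.1:** keep the migraine-day ANCOVA for the primary endpoint, and say that the medication-day test uses the model given for that endpoint in SAP 2.5.
- **Timing:** settle this before the Week 24 unblinding, so that no choice between models is made with results in view.

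The cost is about one sentence in each place and one residual degree of freedom, out of roughly 400 for a pairwise fit or 800 for all arms. The covariate is already in the dataset. If the sponsor prefers to keep the two-term model, it remains valid, and the SAP 3.4.1 cross-reference should still be corrected.
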